2.3.2 Bleed-Related Efficacy Objectives and Endpoints

The key efficacy objective is to characterize the efficacy of 6 mg/kg emicizumab Q4W based on the number of bleeds over time for patients in the expansion cohort.

The bleed-related efficacy objectives are as follows:

- To evaluate the efficacy of prophylactic emicizumab in maintaining adequate control of bleeding based on treated bleeds over time
- To evaluate the clinical effect of prophylactic emicizumab on the number of joint bleeds over time
- To evaluate the clinical effect of prophylactic emicizumab on the number of target joint bleeds over time (target joints are defined as joints with ≥ 3 bleeds occurring in the same joint over the last 24 weeks prior to study entry; see Section 2.3.2.5)
- To evaluate the clinical effect of prophylactic emicizumab on the number of all bleeds (i.e., those treated and untreated with coagulation factors) over time
- To evaluate the clinical effect of prophylactic emicizumab on the number of spontaneous bleeds over time (spontaneous bleed rate)

2.3.2.1 Treated Bleed

A bleed is considered to be a “treated bleed” if it is directly followed (i.e., there is not an intervening bleed) by at least one hemophilia medication reported to be a “treatment for bleed” as specified in the BMQ, irrespective of the time between the treatment and the preceding bleed. A bleed and the first treatment thereafter and before a new bleed starts, are considered to be pairs (i.e., one treatment belongs to one bleed only), with the following exception: if multiple bleeds occur on the same calendar day, the subsequent treatment is considered to apply for each of these multiple bleeds.

Bleeds due to surgery/procedure are not included in the analysis. Only treatments that were recorded as “treatment for bleed” are included in the determination of a treated bleed. Note that a bleed can be treated with more than one treatment.

72-Hour Rule:

Two bleeds of the same type (e.g., “joint,” “muscle,” or “other”) and at the same anatomical location are counted as one bleed if the second bleed occurs within 72 hours from the last treatment for the first bleed. The last treatment is defined as the last treatment associated with the bleed before a new bleed occurs, either in the same or in a different location.

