4.5.8 Bleed Definitions

Definition of a Bleed

For the purpose of the efficacy analyses, a standardized definition of bleed, adapted from criteria defined by the Subcommittee on Standards and Criteria, FVIII/FIX subcommittee of the International Society of Thrombosis and Hemostasis, and similar to that used in a recent clinical study, will be utilized in this study (Blanchette et al. 2014; Mahlangu et al. 2014).

- An event is considered a bleed if coagulation factors are administered to treat signs or symptoms of bleeding (e.g., pain, swelling, etc.). An additional definition of all reported bleeds (irrespective of treatment with coagulation factors) will be applied for a separate analysis.
- Bleeds starting from the first sign of bleed and ending 72 hours after the last treatment for the bleed, within which any symptoms of bleeding at the same location or injections are ≤ 72 hours apart, are considered the same bleed.
- Any injection to treat the bleed, taken > 72 hours after the preceding injection, is considered the first injection to treat a new bleed at the same location.
- Any bleed at a different location is considered a separate bleed regardless of time from last injection.

Definitions of Bleed Sites

- Target joints: defined as a major joint (e.g., hip, elbow, wrist, shoulder, knee, and ankle) into which repeated bleeds occur (frequency of ≥ 3 bleeds into the same joint over the last 24 weeks prior to study entry)
- Joint bleeds are defined as bleeds with bleed type “joint bleed” reported via the bleed/medication questionnaire with at least one of the following symptoms:
 - Increasing swelling or warmth of the skin over the joint
 - Increasing pain
 - Progressive loss of range of motion or difficulty in using the limb as compared with baseline
- Muscle bleeds (sites as per the bleed/medication questionnaire)
- Other (sites as per the bleed/medication questionnaire)

Definitions of Bleed Types

In addition, the assessment of a bleed will be separated into spontaneous bleeds, traumatic bleeds and bleeds related to procedure/surgery. Both spontaneous bleeds (i.e., the occurrence of hemorrhage where neither the patient nor a caregiver can identify a reason) and traumatic bleeds (i.e., hemorrhage occurring secondary to an event such as trauma, “strenuous” activity, or “overuse”) will be collected.

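### The treated-bleed pairing rule in SAP 2.3.2.1 can drop the first of two bleeds at different sites that start on consecutive calendar days and share one infusion; the net effect on the ABR is unknown.

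*SAP*

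**What the plan says.** SAP 2.3.1 says the primary analysis counts bleeds that were treated with coagulation factors and meet the adapted ISTH criteria in protocol 4.5.8. It then refers to more specific rules in the sections that follow.

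SAP 2.3.2.1 supplies those rules:
- A bleed is treated if it is "directly followed (i.e., there is not an intervening bleed) by at least one hemophilia medication" recorded as given for a bleed, "irrespective of the time between the treatment and the preceding bleed".
- Bleeds and treatments form pairs: "one treatment belongs to one bleed only".
- There is one exception: "if multiple bleeds occur on the same calendar day, the subsequent treatment is considered to apply for each of these multiple bleeds".
- Two bleeds of the same type and location merge if the second starts within 72 hours of the last treatment for the first. That last treatment is "the last treatment associated with the bleed before a new bleed occurs, either in the same or in a different location".

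Protocol 4.5.8 has no pairing and no calendar-day condition:
- "An event is considered a bleed if coagulation factors are administered to treat signs or symptoms of bleeding".
- "Any bleed at a different location is considered a separate bleed regardless of time from last injection".
- At one location, a bleed runs from its first sign to 72 hours after its last treatment, "within which any symptoms of bleeding at the same location or injections are ≤ 72 hours apart, are considered the same bleed".

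The same protocol section says that patients report, for each bleeding episode, the medication used to treat it.

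**The concern.** Take a knee bleed on Monday at 22:00, an elbow bleed on Tuesday at 06:00, and one infusion on Tuesday at 07:00 given for both. The elbow bleed intervenes between the knee bleed and the infusion, and the two start on different dates, so under the SAP the knee bleed is not treated. If the knee bleed had started at 00:30 on Tuesday, both would count. The same-day exception accepts that one infusion can treat several bleeds, but the SAP gives no reason for ending that at midnight.

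Treated bleeds are the primary count. The joint, target-joint and spontaneous endpoints (SAP 2.3.2.3 to 2.3.2.5) are selected from them, so a dropped bleed leaves those as well. The study has no hypothesis test, so the estimated ABR and its interval are the efficacy result. The SAP plans no sensitivity analysis of the pairing.

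**Working it through.** The plan states no figure that depends on this rule, so there is none to reproduce. The check applies both definitions to the same event patterns and then sets a scale.

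**Counts under each definition (recorded bleeds)**

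| Pattern | SAP 2.3.2.1 | Protocol 4.5.8 |
|---|---|---|
| 1. Consecutive days, different sites, one infusion for both | 1 | 2 |
| 2. As 1, infusion for the second bleed only | 1 | 1 |
| 3. Consecutive days, same site, one infusion | 1 | 1 |
| 4. Same day, different sites, infusion for both | 2 | 2 |
| 5. Same day, different sites, infusion for one only | 2 | 1 |
| 6. First bleed infused before the second starts | 2 | 2 |
| 7. Untreated bleed; unrelated treatment entry 20 days later with no bleed entry of its own | 1 | 0 |
| 8. Knee bleed treated on day 0; elbow bleed on day 1; infusions for both to day 3; knee symptoms again on day 4 | 3 | 2 |

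Pattern 1 is the undercount. Patterns 5, 7 and 8 are overcounts, from same-day sharing, the missing time limit and the truncated last treatment. In pattern 8 the elbow bleed ends the first knee bleed's treatments on day 0, so the day 4 symptoms fall outside 72 hours. Pattern 7 is an overcount only if the later entry did not treat a real bleed that went unrecorded.

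**Scale of one lost bleed**

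Inputs: 40 expansion patients (SAP 2.4), 24 weeks = 168 days as the planned minimum (SAP section 2), and ABR = bleeds / days × 365.25 (SAP 4.5.1).
- One patient: 365.25 / 168 = 2.17.
- Cohort, bleeds over total time: 365.25 / (40 × 168) = 365.25 / 6,720 = 0.054.

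The efficacy period runs to the clinical cutoff, so follow-up beyond 168 days makes both figures smaller.

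**How often, if bleeds are independent**

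Assume a daily rate r = ABR / 365.25, uniform start times, and a delay D in days from bleed to infusion. Assume also that every next bleed is at a different site and that the infusion is given for both. A gap of g days (g below 1) crosses midnight with probability g. The share of bleeds lost is therefore about r × D²/2 for D up to 1 day, and about 1.5r for D = 2.
- ABR 1 (r = 0.00274): 0.01% at D = 0.25; 0.4% at D = 2.
- ABR 10.9 (r = 0.0298): 0.1% at D = 0.25; 4.3% at D = 2 by simulation (the approximation gives 4.5%).

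The upper ABR is the entry minimum for episodic patients: 5 / 168 × 365.25 = 10.87.

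**If bleeds cluster**

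If 5% to 20% were lost (assumed), a true ABR of 2.5 would read 2.5 × 0.95 = 2.38 to 2.5 × 0.80 = 2.00. The documents give no basis for choosing a value.

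**The case against.** The strongest reply is that this is a narrow case in a descriptive study, and that the SAP rule is a workable way of applying the protocol. Several parts of that stand.

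- The protocol definition turns on purpose: factor given to treat the signs or symptoms of that bleed. If the infusion was meant only for the second bleed, the SAP count is right (pattern 2). That one infusion acts on every open bleed is a pharmacological argument, not the protocol's definition.
- At the same site within 72 hours, both documents count one bleed (pattern 3).
- With independent bleeds the loss is small at low rates. The simulations in protocol 3.3.1 suggest a median ABR of 1 at troughs of at least 16 µg/mL.
- The dropped bleed can still enter the all-bleeds endpoint (SAP 2.3.2.2). The backstop is partial: the 72-hour rule for non-treated bleeds states no location condition, so a bleed soon after an earlier treatment could be dropped there too.
- A date-based rule works when times are missing, and SAP 4.9 allows blank times in the site entry system. The SAP does not give this as its reason.

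None of this reconciles pattern 1 with protocol 4.5.8, which SAP 2.3.1 says the primary count follows.

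**Conclusion.** The SAP can undercount treated bleeds against the protocol in one defined pattern: different sites, consecutive start dates, one infusion given for both after the second bleed starts. Each such bleed costs 2.17 on that patient's 168-day ABR and about 0.054 on the 40-patient, 24-week rate. No success decision depends on it, but the treated-bleed estimates do.

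A reader might infer that the primary ABR is biased low overall, or that the error runs one way. The documents do not support that. The same section can also overcount, and no frequencies are given to net the two.

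A reader might also attach a percentage. If a fraction f of counted bleeds is assumed to have a lost predecessor, the understatement is f/(1 + f), or 2% to 9% for f between 2% and 10%. That only restates the assumption. For pairs 4, 8 or 12 hours apart with uniform starts, gap/24 gives 17%, 33% or 50% straddling midnight. Those shares do not say how many such pairs occur.

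**What to change.** Where the per-episode medication data described in protocol 4.5.8 show which bleeds an infusion was given for, use that link to decide treated status. The documents do not show whether the stored data always hold the link, so the SAP should say what happens when they do not.

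In that case, keep the present rule and add a pre-specified sensitivity analysis. It would also credit an infusion recorded as given for a bleed to every not-yet-treated bleed at a different site that started within a stated window before it. The window could be 72 hours, with a date-only fallback when a time is blank. The SAP should present this window as a new choice, because the plan's existing 72-hour rules merge or separate bleeds and do not link an infusion back to earlier bleeds at other sites. The same-location merge stays. Report how many bleeds change status and the resulting ABR with 95% CI.

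The cost is SAP wording and some derivation work, with no new data collection. The downside is that the sensitivity ABR may include a minor earlier bleed that the patient did not mean to treat.

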2.2 COLLECTION OF PATIENT-REPORTED DATA

2.2.1 Collection of Bleed and Medication Data

Bleed and medication data are collected through a bleed and medication questionnaire (BMQ), which was developed by the Sponsor given that no standard questionnaire for collection of this data was available. The BMQ was developed as a patient-reported measure of bleeding episodes (including cause, type, location, and symptoms of bleeds) and hemophilia-related medication use. This questionnaire was initially used in the non-interventional study (NIS; BH29768), patients with inhibitors study (BH29884), and later in the studies for pediatric patients (Study BH29992) and the non-inhibitor patients (Study BH30071).

To capture bleed data, emicizumab use, and other hemophilia medication use during study treatment, patients will complete the BMQ on a handheld device that will be provided to them during the Week 1 visit at the study site. This device will remain with the patient for the duration of the study to enter bleed and medication data weekly at a minimum. In case a patient did not experience any bleeds or administer any treatments for a week, the patient is asked to log into the device and fill in the questionnaire to confirm this. These weekly entries, in addition to the bleeds and medication entries can also be used to assess compliance. Of note, the patient is able to enter bleeds and medications for the past 8 days, including the day the entries are made. This retrospective data entry window was considered acceptable in terms of recall bias and was added in order to optimize the completeness of data collection.

Patients who withdraw from emicizumab treatment will continue to record bleeds and hemophilia medication administration until they complete the safety follow-up visit.

The patient is able to edit and delete bleeds and medications for 24 hours after they are entered. Furthermore, the investigator and patient are instructed to review the data together at every clinic visit. If the patient has been unable to enter data for any reason, the investigator is able to do so using a data clarification request (Data Change Request [DCR]; not subject to the previous 8-day data entry window). Note, the symptoms of joint and muscle bleeds are not collected in this case because the patient may not be

able to reliably remember them. In addition, the investigator is able to request a change be made to the vendor's database by submitting a DCR.

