Furthermore, the Sponsor's data manager and Medical Monitor review the patient entered data for clear inconsistencies against data collected on the electronic Case Report Form (eCRF) or to identify obvious data points to be clarified (e.g., missing entry of the weekly emicizumab injection). These requests are sent to the investigator, who reviews them with the patient and may enter the data via the site data entry system or request a change to be made in the vendor's database via a DCR, if necessary.

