2.3 OBJECTIVES AND ENDPOINTS

2.3.1 Efficacy Period for All Endpoints

The start of the efficacy period for each individual patient is defined as the date of first emicizumab administration.

The end of the efficacy period is defined as the date of the clinical cutoff or the date of withdrawal from the initial study period (i.e., treatment phase according to eCRF-Subject Disposition page), whichever is earlier. For patients whose dose is up-titrated, the efficacy period ends a day prior to the first day on the up-titrated dose.

The efficacy period on a given up-titrated/down-titrated dose starts with the first day on this dose and ends on the date of the clinical cutoff or the date of withdrawal or date preceding the next up-titration/down-titration. Bleeds on the up-titrated/down-titrated dose are analyzed separately (see Section [4.1](#)).

Bleed rate is defined as the number of bleeds over the efficacy period. A bleed is counted in the primary analysis if it was treated with coagulation factors and fulfills the adapted International Society on Thrombosis and Haemostasis (ISTH; [Blanchette et al. 2014](#)) criteria, as described in Section 4.5.8 of the protocol. More specifically, the rules outlined in the sections below are applied.

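### SAP 2.3.2.1 carries only the merging half of the protocol's 72-hour bleed definition, so a late re-treatment with no new diary entry is not counted as a new bleed

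*SAP*

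**What the plan says.** Protocol 4.5.8 defines a bleed with two 72-hour rules. The first merges: symptoms at one location, or injections, no more than 72 hours apart belong to one bleed. The second splits: an injection to treat the bleed taken more than 72 "hours after the preceding injection, is considered the first injection to treat a new bleed at the same location". The splitting rule does not require a new diary entry.

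SAP 2.3.1 says a bleed counts in the primary analysis if it meets the adapted ISTH criteria "as described in Section 4.5.8 of the protocol". It then says that the specific rules in its following sections are the ones applied.

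SAP 2.3.2.1 starts from diary entries:
- A treatment is linked to the entry before it "irrespective of the time between the treatment and the preceding bleed".
- Several treatments may belong to one bleed: "Note that a bleed can be treated with more than one treatment".
- Two entries of the same type and site are "counted as one bleed if the second bleed occurs within 72 hours from the last treatment for the first bleed".
- The last treatment is "the last treatment associated with the bleed before a new bleed occurs, either in the same or in a different location".

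SAP 2.3.2.2 uses the same rule for the treated part of the all-bleeds endpoint. SAP 2.3.2.3 to 2.3.2.5 draw the spontaneous, joint and target-joint subsets from treated bleeds.

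**The concern.** The SAP rule needs two recorded entries before the 72-hour window does anything. It cannot create a bleed from an injection. If a patient treats a knee bleed, treats it again six days later and makes no new entry, protocol 4.5.8 gives two bleeds and SAP 2.3.2.1 gives one.

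There is a second effect. If the late injection is attached to the old bleed, it moves that bleed's last treatment later. A further entry at the same site can then fall within 72 hours of it and be merged.

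The treated-bleed rate in the expansion cohort is the key efficacy result of a single-arm study, so no control group absorbs a counting difference. Both effects act in the direction of a lower rate.

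**Working it through.** **Counts.** The plan states no figure to reproduce, so I applied each document's rule to hypothetical single-site diaries. The last column adds this sentence to the SAP: a treatment more than 72 hours after the preceding treatment for that bleed starts a new treated bleed.

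| Diary (knee) | Protocol 4.5.8 | SAP 2.3.2.1 | SAP + sentence |
|---|---|---|---|
| Entry Day 1; injections Days 1, 2, 8 | 2 | 1 | 2 |
| As above, plus a new entry on Day 8 | 2 | 2 | 2 |
| Entry Day 1; injections Days 1, 2, 8; then entry and injection Day 10 | 2 | 1 | 2 |
| One entry; injections Days 1, 8, 15 | 3 | 1 | 3 |
| One entry; injections Days 1, 2, 4 | 1 | 1 | 1 |

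Row 2 shows that the documents agree when the patient makes a new entry. Row 3 shows the second effect. Without the Day 8 injection, the Day 10 entry is 8 days after the last treatment and the SAP counts 2. With it, the gap is 2 days and the SAP counts 1.

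**Size per event.** Inputs: 40 expansion patients (SAP 2.4), 24 weeks = 168 days (SAP 2.5), and the ABR formula in SAP 4.5.1.
- One patient, 24 weeks: 1 / 168 × 365.25 = 2.17.
- All 40 patients, each followed 24 weeks: 2.174 / 40 = 0.054.
- At 48 weeks: 365.25 / 336 = 1.09, and 1.087 / 40 = 0.027.

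**Relative size.** Let f be the number of uncounted late re-treatments per SAP-counted treated bleed. The SAP rate falls short of the protocol-rule rate by f / (1 + f), whatever the follow-up. The documents do not give f. Assumed values of 0.02, 0.05 and 0.10 give 2.0%, 4.8% and 9.1%.

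**Zero-bleed patients.** The splitting rule acts only after an earlier injection for a recorded bleed, and the SAP already counts that bleed. The set of patients with no treated bleeds is therefore the same under both rules.

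**Two cases the added sentence does not settle.**
- Knee and elbow are both entered on Day 1, with injections on Days 1 and 8. SAP 2.3.2.1 lets one treatment serve all same-day bleeds, and the treatment details listed in protocol 3.1.2 do not include a site. The sentence alone could turn one late injection into two new bleeds.
- Injection at 0 h, same-site entry at 60 h, injection at 80 h. The SAP merges these into 1 bleed. In protocol 4.5.8 the merging rule points to 1 (symptoms at 60 h) and the splitting rule to 2 (injections 80 h apart).

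**Non-treated bleeds (SAP 2.3.2.2).** The sentence names no location and joins its two 72-hour conditions with an or. Take untreated knee bleeds on Days 1 and 3, with the last treatment four weeks earlier. Requiring both conditions gives 1 bleed; requiring either gives 2. The protocol suggests 1, but only by inference, because its window is timed from treatment.

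**The case against.** The best reply is incorporation by reference. SAP 2.3.1 invokes protocol 4.5.8, and SAP 2.3.2.1 pairs treatments with a bleed only until a new bleed starts, without defining a new bleed. If 4.5.8 supplies that definition, the late injection closes the old bleed and nothing is lost. This reading is possible. But SAP 2.3.1 makes its own following sections the applied rules, and 2.3.2.1 contains no step that yields the extra bleed. A programmer who follows it will not count one.

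The second reply is data review. Under SAP 2.2.1 "the investigator and patient are instructed to review the data together at every clinic visit", and the sponsor's data manager and Medical Monitor "review the patient entered data for clear inconsistencies". Protocol 4.5.8 also refers to a Medical Data Review Plan that is not among the documents. Review may well prompt a new entry, in which case the counts agree. Nothing available says that this pattern is queried, or that it is not.

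Third, the SAP appends the Version 2 synopsis, while the protocol at hand is Version 5. The available part of the Version 5 change list does not name 4.5.8, but the Version 2 text cannot be checked. The SAP may have matched the text it was written against.

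A reader might infer that the reported ABR is materially too low, or that a favourable count was chosen on purpose. The documents support neither. They give no frequency of late re-treatment, and the omission may be no more than a drafting gap.

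On SAP 2.3.2.2, the 72-hour rule it implements is already same-site in 2.3.2.1, so the missing location is probably a drafting omission.

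**Conclusion.** The point holds as a mismatch between the operative SAP algorithm and the protocol definition it cites. Followed as written, SAP 2.3.2.1 does not count a late re-treatment that has no new entry. Taken alone, the omission leaves the treated-bleed ABR unchanged or lowers it, and can do the same to the spontaneous, joint and target-joint subsets.

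The per-event values of 2.17 and 0.054 assume exactly 24 weeks of follow-up, in all 40 patients for the second. SAP 2.3.1 runs the efficacy period to the clinical cutoff, so patients followed longer contribute less per event. The 2.0% to 9.1% range rests wholly on assumed frequencies.

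A reader might also expect the proportion of patients with zero treated bleeds to be flattered; it is not affected. The efficacy analysis is descriptive, so no test result is at risk. The correction is worth making because it is specific and cheap and concerns the key efficacy count. The SAP 2.3.2.2 wording is a minor clarification.

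**What to change.** In SAP 2.3.2.1, add that a treatment for bleed given more than 72 hours after the preceding treatment for that bleed starts a new treated bleed of the same type and location. Keep the same-type condition in the merging rule. State three conventions with it:

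- **Shared treatments.** Where the earlier treatment served same-day bleeds at several sites, one late injection adds at most one new bleed unless its site is recorded.
- **Conflicting windows.** Say how to count a same-site entry within 72 hours whose injection comes more than 72 hours after the previous one.
- **Blank times (allowed by SAP 4.9).** Use dates. Four or more calendar days apart is over 72 hours and two or fewer is not. Three days (48 to 96 hours) needs a stated choice.

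Report the treated-bleed ABR under the present algorithm as a sensitivity analysis. Report the spontaneous and joint subsets (including target joint) with and without carrying over the first entry's cause and symptoms, since neither is recorded for a bleed created by the program.

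In SAP 2.3.2.2, state that the 72-hour conditions for non-treated bleeds apply at the same location, and whether both must hold.

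No new data are needed, because protocol 3.1.2 already asks for the start time of each treatment. The cost is some reprogramming, a few extra summaries, and an ABR that stays the same or rises slightly.
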